Research Question: Are BSCVA outcomes, endothelial cell counts, and post-operative corneal light scatter and higher-order aberrations different between patients undergoing ultrathin DSAEK versus DMEK?

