1.1 Specific Aims

- 1) **To determine whether there is a difference in best spectacle-corrected visual acuity (BSCVA) at 6 months between patients receiving ultrathin DSAEK and DMEK.** We hypothesize that the DMEK group will have improved visual acuity compared with DSAEK at 3 months, but not at 6 months. By randomizing 25 patients per arm, we anticipate 80% power to detect a one standard deviation, or approximately 1.2 Snellen lines, difference in BSCVA between the DMEK and DSAEK groups.
- 2) **To evaluate endothelial cell loss at 6 months between patients receiving ultrathin DSAEK and DMEK.** We hypothesize that there will be a difference in endothelial cell loss at 6 months between patients receiving ultrathin DSAEK and DMEK, accounting for pre-operative endothelial cell count.
- 3) **To assess the relative role of light scatter, higher-order aberrations and graft thickness on visual acuity.** We predict that there will be increased light scatter at the

graft-host interface and but no difference in posterior corneal higher-order aberrations of the central 4mm in DSAEK versus DMEK.¹⁰

While long-term outcomes such as graft rejection and survival are beyond the scope of the initial phase of this study, we anticipate we will be able to evaluate these as we follow patients at 12 and 24 months.

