3. PATIENT FLOW

3.1 Study Timeline

The enrollment period will be 24 months. Study participants will be required to have follow-up visits at months 3 (visit window: 2-4 months), 6 (visit window: 5-7 months), 12 (visit window: 10-14 months), and 24 (visit window: 20-28) from the time of surgery. Additional visits may be needed and will be determined by the surgeon/investigator.

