3.4 Study Visits

3.4.1 Baseline Visit

During this visit, eligible patients who are enrolling for the first time will be enrolled in the study and will give consent. The baseline patient form will be completed and the NEI-VFQ will also be administered. If a patient includes a second eye in the study, they will complete an abbreviated baseline patient form for that study eye prior to surgery. They will not complete a second NEI-VFQ at the baseline visit for their second eye. Patients will also complete BSCVA, IOP, Pachymetry, and Pentacam tests at baseline.

3.4.2 *Surgery Visit*

The enrolled study participant's eye(s) will undergo either DSAEK or DMEK surgery. If both of a participant's eyes are included in the study, randomization to DSAEK or DMEK will be performed independently for each eye.

3.4.3 *Follow-Up Visits*

The follow-up patient form will be completed at each visit, for each enrolled eye. Data collected for each follow-up visit will include:

3 month follow-up: BSCVA, IOP, pentacam topography and densitometry pachymetry, optical coherence tomography, and endothelial imaging will be performed. The NEI-VFQ form will also be completed

6 month follow-up data: BSCVA, IOP, pentacam topography and densitometry pachymetry, optical coherence tomography, endothelial imaging, and slit-lamp photography will be performed.

12 month follow-up: BSCVA, IOP, pentacam topography and densitometry pachymetry, optical coherence tomography, and endothelial imaging will be performed. The NEI-VFQ form will also be completed

3.4.4 *Final Visit*

During the Month 24 final visit, the final status and follow-up patient forms will be completed. BSCVA, IOP, pentacam topography and densitometry pachymetry, optical coherence tomography, and endothelial imaging will also be performed.

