As a methodological sensitivity analysis, we will conduct ANCOVA with ranks (which becomes the Wilcoxon rank sum test in the post-test only case). Model checking will be conducted for the primary analysis (and for all secondary analyses) based on analysis of residuals versus fitted values. We will conduct leave-one-out influence analysis to locate highly influential observations (a procedure we will apply to secondary analyses also). Individuals with missing six month data will be included based on last observation carried forward from the 3 month records; individuals with no follow-up data cannot be included but will be tabulated. Sensitivity analysis of missing values will be conducted to assess the range of values of missing observations that would be needed to change the results of the hypothesis test.

Protocol for measuring BCSVA is outlined in the MOP. BSCVA will be analyzed using an intent to treat analysis, with all eyes that are randomized being analyzed at 6 months regardless of subsequent surgery or graft failure. We will tabulate results by study site.

One safety analysis will be performed. No interim efficacy or futility analysis will be conducted.

5. Secondary Analyses

Key secondary outcomes

- We will analyze endothelial cell counts controlling for baseline endothelial cell count measured at the eye bank using mixed effect multiple linear regression conducted
- NEI-VFQ will be compared between the two groups with multiple linear regression, controlling for baseline VFQ.
- Three-month BCVA will be analysed using the same procedure as the primary outcome.
- A linear mixed model will be used in which both three and six month data are modeled, with a random intercept for eye, and with time, baseline BCVA, and treatment assignment as fixed effects. A graft rejection episode will be defined as loss of graft clarity due to edema with evidence of inflammation such as anterior chamber cell or keratic precipitates, and will be compared between the two groups using Fisher's exact test.
- For the purposes of this study, primary graft failure will be defined as a lack of graft clearing or need for re-graft within the first 2 months, and will be compared between the two groups using Fisher's exact test.

Supplementary secondary outcomes

- A pre-specified non-inferiority threshold is set at a 0.1 logMAR difference in visual acuity.

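### No analysis in the supplied SAP uses month 12 or 24 BSCVA, and the month 3 and 6 mixed model has no treatment-by-time term, so the change over time that Aim 1 predicts is not estimated.

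*SAP*

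**What the plan says.** **What is measured.** Protocol 3.1 makes visits at months 3, 6, 12 and 24 a requirement ("Study participants will be required to have follow-up visits at months 3", and the sentence goes on to list the other three). BSCVA is taken at each. For month 12, Protocol 3.4.3 has "12 month follow-up: BSCVA, IOP, pentacam topography and densitometry pachymetry, optical coherence tomography, and endothelial imaging will be performed". For month 24, Protocol 3.4.4 has "During the Month 24 final visit, the final status and follow-up patient forms will be completed. BSCVA, IOP, pentacam topography and densitometry pachymetry". Protocol 4.3 and Table 1 agree.

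**What is analysed.** SAP section 5 describes the longitudinal model thus: "A linear mixed model will be used in which both three and six month data are modeled, with a random intercept for eye", "with time, baseline BCVA, and treatment assignment as fixed effects". The other acuity analyses in SAP sections 4 and 5 are set at month 6 or month 3.

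**What is aimed at.** The research question is open in time: "Are BSCVA outcomes, endothelial cell counts, and post-operative corneal light scatter and higher-order aberrations different between patients". Aim 1 in Protocol 1.1 is narrower. It concerns BSCVA at 6 months and expects DMEK to do better at 3 months but not at 6. Protocol 1.1 also says that long-term outcomes, of which "graft rejection and survival are beyond the scope of the initial phase of this study" gives two examples, are expected to be evaluated at months 12 and 24. It gives no method.

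**The concern.** There are two linked gaps.

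First, Aim 1 states a treatment effect that changes between months 3 and 6. The one model that holds both visits is written so that the effect must be the same at both. It can report an average difference but not whether the difference shrinks.

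Second, two of the four scheduled post-operative acuity readings have no planned comparison. Once the 6-month result is known, whether the arms stay together or separate is the natural next question for a trial that the SAP describes as finding the surgery with the better visual outcome. If the model, the handling of missed visits and the handling of re-grafted eyes are all chosen after that result is seen, the later comparison is post hoc and will be read as such.

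**Working it through.** **Step 1. Set the acuity analyses against the visits.**

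| Acuity analysis in the SAP | Month 3 | Month 6 | Month 12 | Month 24 |
|---|---|---|---|---|
| Primary ANCOVA (section 4) | | yes | | |
| ANCOVA on ranks (section 4) | | yes | | |
| Three-month ANCOVA (section 5) | yes | | | |
| Linear mixed model (section 5) | yes | yes | | |
| LOCF after primary graft failure (section 5) | | yes | | |
| Kolmogorov-Smirnov test (section 5) | | yes | | |
| BSCVA scheduled (Protocol 3.4.3, 3.4.4, Table 1) | yes | yes | yes | yes |

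The 0.1 logMAR non-inferiority threshold in SAP section 5 has no time point. SAP section 6 adds no later acuity comparison, and Protocol section 8 leaves all statistical detail to the SAP.

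**Step 2. What the mixed model estimates.** Let D3 and D6 be the treatment differences at months 3 and 6. With every eye seen at both visits, the model's treatment coefficient is (D3 + D6)/2. As an illustration, use the SAP's detectable difference of 0.12 logMAR:

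- Aim 1's pattern, D3 = 0.12 and D6 = 0: (0.12 + 0)/2 = 0.06.
- A constant effect, D3 = D6 = 0.06: (0.06 + 0.06)/2 = 0.06.

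Both patterns give the same coefficient, so it cannot tell a vanishing effect from a steady one. Extending this model to months 12 and 24 without an interaction would only average over more visits.

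**Step 3. The plan's own figure.** SAP section 2 gives 80% power at 25 eyes per arm for a difference of 0.12 with SD 0.12. The standard error is 0.12 × √(2/25) = 0.0339, and 0.12/0.0339 = 3.54. At two-sided alpha 0.05 the power is Φ(3.54 − 1.96) = 94.2% (93.4% with the t distribution). The stated 80% is not reproduced, but the mismatch is conservative and has no bearing on this point.

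**Step 4. How precise the later contrasts would be.** The documents give no SD or attrition rate for months 12 or 24. Assume that the 6-month SD of 0.12 holds and that eyes are independent. The unadjusted 95% half-width is t(0.975, 2n − 2) × 0.12 × √(2/n):

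- n = 25 per arm: 2.011 × 0.0339 = 0.068 logMAR
- n = 22 (3 of 25 lost, 12%): 2.018 × 0.0362 = 0.073
- n = 17 (8 of 25 lost, 32%): 2.037 × 0.0412 = 0.084

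**Step 5. How precise a change in the treatment difference would be.** For a change between two visits, the SD becomes 0.12 × √(2(1 − ρ)), where ρ is the within-eye correlation. With ρ assumed to be 0.5 to 0.7, the half-width is 0.068 to 0.053 at 25 per arm and 0.084 to 0.065 at 17.

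**The case against.** The case for the plan as written has real force.

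- **Scope.** Aim 1 and the primary outcome stop at 6 months, and no later BSCVA appears among the secondary or other outcomes in Protocol 1.2. Measuring something at visits that are part of normal care does not make it a declared outcome. This stands, and it keeps the point secondary. Still, Protocol 1.2 includes change in NEI-VFQ to 12 months, so month 12 is not out of scope for visual function.
- **Deferral.** A reader might infer that Protocol 1.1 defers only graft rejection and survival, leaving acuity in the present phase. The text does not support that: those two are introduced as examples, and later acuity is neither clearly included nor clearly excluded. But the deferral gives no method and cites no later SAP.
- **Other analyses.** A reader might infer that the later readings enter no analysis at all. That cannot be established. A separate cost-effectiveness SAP is cited but not among the documents, and the protocol's introduction expects further secondary analyses. The claim is limited to the supplied SAP.
- **Months 3 and 6 separately.** The two ANCOVAs do give a treatment difference at each visit. However, a significant result at one visit and a non-significant result at the other is not a test that the difference changed.
- **Precision.** The later SD is assumed. Both eyes of one participant may be enrolled, so independence is an assumption too. A half-width below 0.1 logMAR does not itself show non-inferiority.

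**Conclusion.** The point holds as a secondary gap in prespecification. The supplied SAP does not say whether or how month 12 and 24 BSCVA will be compared, and its mixed model cannot show the change over time in Aim 1. The primary 6-month test, the sample size and the three-month analysis are unaffected.

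A reader might go further and conclude that the trial cannot say whether a 6-month difference, or its absence, lasts. The documents do not support that. Eyes are randomised and the readings are scheduled, so the later differences can be estimated. What is missing is an analysis fixed in advance.

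The later contrasts would be about as precise as the 6-month one if few eyes are lost: roughly ±0.07 logMAR, widening to about ±0.08 at 17 eyes per arm. This rests on SD 0.12 logMAR persisting beyond month 6 and on independent eyes.

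**What to change.** In SAP section 5:

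1. Keep the month 3 and 6 mixed model, but enter visit as a category and add a treatment-by-visit term. Report the treatment difference at each visit and the change between visits. This version can be reported on time, without waiting for later visits.
2. Before the 6-month results are known, prespecify an extension of the same model to months 12 and 24. Report each treatment difference with a 95% CI, labelled secondary or exploratory.
3. State the data rules for the extension. All randomised eyes stay in regardless of re-graft, as in the primary intention-to-treat rule, and no values are carried forward to months 12 or 24.
4. Leave the month 6 ANCOVA as the single primary test.

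The cost is SAP wording and modest extra analysis, with no new visits or measurements. The downside is two more secondary contrasts, available only when the later visits finish.

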1.3 Study Design

Descemets Endothelial Thickness Comparison Trial (DETECT) is a randomized double-masked, two-arm clinical trial. The purpose of this study is to determine differences in visual outcomes between two types of corneal transplant surgeries. There will be 1:1 randomization to one of two treatment groups – 1.) Ultrathin Descemet's Stripping Endothelial Keratoplasty (DSAEK) OR 2.) Descemet's Membrane Endothelial Keratoplasty (DMEK). The enrollment period is 24 months.

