Descemet's Endothelial Thickness Comparison Trial

Statistical Analysis Plan

Francis I. Proctor Foundation, University of California San Francisco
Casey Eye Institute, Oregon Health & Science University
Byers Eye Institute, Stanford University

Investigators:

[name], PhD¹
[name], PhD*²
[name]*²
[name]*³
[name], COT²
[name], MS¹

*Principal Investigator

¹Casey Eye Institute, Oregon Health & Science University, Portland, Oregon

² Francis I. Proctor Foundation, University of California San Francisco, San Francisco, California

³Byers Eye Institute, Stanford University, Palo Alto, California

DETECT Statistical Analysis Plan

Table of Contents

1. Background	1
2. Sample Size and Randomization.....	1
3. Baseline Characteristics	1
4. Primary Analysis.....	1
5. Secondary Analyses	1
6. Other Data.....	2

1. Background

Descemets Endothelial Thickness Comparison Trial (DETECT) is a randomized, double-masked, two-arm clinical trial. The purpose of this study is to determine which of two types of corneal transplant surgeries has the better visual outcome. Study participant's eyes will be randomized to one of two treatment groups – 1.) Ultrathin Descemet's Stripping Endothelial Keratoplasty (DSAEK) or 2.) Descemet's Membrane Endothelial Keratoplasty (DMEK).

2. Sample Size and Randomization

We anticipate that 25 eyes per arm would provide 80% power to detect a 0.12 logMAR difference (approximately 1.2 Snellen lines), assuming two-tailed alpha, and a standard deviation of best spectacle-corrected visual acuity (BSCVA) at 6 months of 0.12 logMAR (approximately 1.2 Snellen lines) at 6 months. Participant's eyes will be randomized using random block sizes in Microsoft Excel ([name]).

3. Baseline Characteristics

Baseline characteristics between the 2 arms will be compared using Fisher exact test for categorical variables and Wilcoxon rank sum test for continuous variables.

4. Primary Analysis

For the primary study analysis, we will compare BSCVA between the two groups at the 6-month time period (between 5-7 months) using ANCOVA, with baseline BCVA and treatment group as covariates. Statistical significance will be assessed by permutation with a two-sided alpha of 0.05. (If the correlation coefficient between baseline BCVA and 6 month BCVA has magnitude less than 0.1, we will omit the variable entirely, yielding a post-test only analysis).

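### Boschloo's exact test would be a cheap improvement on Fisher's for graft failure and rejection: it recovers part of the power that Fisher gives up at 25 eyes per arm, though how much depends on the final arm sizes

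*SAP*

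**What the plan says.** SAP section 5 lists both outcomes under its key secondary outcomes. For primary graft failure the text is "need for re-graft within the first 2 months, and will be compared between the two groups using Fisher's exact test". For graft rejection it ends "keratic precipitates, and will be compared between the two groups using Fisher's exact test". No other between-arm test, effect estimate or interval is specified for either outcome.

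The numbers of eyes come from SAP section 2, "25 eyes per arm would provide 80% power to detect a 0.12 logMAR difference", and Protocol 1.3, "There will be 1:1 randomization to one of two treatment groups". That power statement concerns 6-month BSCVA only. Neither document gives an expected event rate, a power or a significance level for graft failure or rejection. The only stated level is the one for the primary analysis in SAP section 4: "Statistical significance will be assessed by permutation with a two-sided alpha of 0.05". Protocol 3.4.2 allows both eyes of a participant to enter, each randomised independently.

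**The concern.** With few events, Fisher's p-value moves in large steps because it conditions on the total number of events. A nominal 5% test can then have a true size far below 5%, and the unused error rate is lost power. At 25 eyes per arm, a split of 5 failures against 0, which is 20 percentage points, would just miss significance.

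These are the only planned between-arm tests of graft failure and rejection. Protocol 6.3 itself says that graft rejection, graft survival and donor attachment may differ between the procedures. Another exact test keeps the 5% limit and gives up less.

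**Working it through.** **The plan's own figure.** There is none for these two outcomes. The 80% in SAP section 2 rests on a BSCVA difference and SD of 0.12 logMAR each. At two-sided 0.05 those inputs give Φ(√(25/2) × 0.12/0.12 − 1.96) = Φ(1.576) = 94%, not 80%. That is a separate matter and does not enter here.

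**Inputs.** From the documents: 25 eyes per arm, 1:1, Fisher's test. Assumed: two-sided 0.05 for these comparisons, independent eyes for the main figures, and all event rates.

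**Step 1: Fisher p-values with no events in one arm.** With equal arms of 25 and k events all in one arm, p = 2 × C(25,k)/C(50,k).
- k = 5: 2 × 53,130/2,118,760 = 0.0502, not significant.
- k = 6: 2 × 177,100/15,890,700 = 0.0223, significant.

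So Fisher needs 6 against 0 (24% versus 0%).

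**Step 2: Boschloo's p-value.** Let p_F(a,b) be the two-sided Fisher p-value for a and b events. Boschloo's p-value is the maximum, over a common rate π, of P_π{p_F(A,B) ≤ p_F(a,b)}, with A and B independent Binomial(25, π). For 5-0 it is 0.033 and for 6-0 it is 0.013. It never exceeds p_F, so every Fisher rejection is kept. Tables gained include 5-0, 8-2 (p = 0.041) and 10-3 (p = 0.033).

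**Step 3: true size.** Sum Bin(a; 25, π) × Bin(b; 25, π) over all 26 × 26 tables with p ≤ 0.05.

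| Common rate | Fisher | Boschloo |
|---|---|---|
| 2% | 0.001% | 0.015% |
| 5% | 0.08% | 0.41% |
| 10% | 0.88% | 1.9% |
| 20% | 2.2% | 3.8% |
| Maximum over all rates | 3.3% | 4.6% |

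Fisher's size first passes 1% at a rate of about 10.5%, Boschloo's at about 7%.

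**Step 4: power at 25/25.** Use the same sum with a different rate in each arm. For 0% versus 20% it reduces to one binomial tail with X ~ Bin(25, 0.2): Fisher P(X ≥ 6) = 38.3%, Boschloo P(X ≥ 5) = 57.9%.

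| Assumed rates | Fisher | Boschloo |
|---|---|---|
| 0% vs 10% | 3.3% | 9.8% |
| 2% vs 10% | 2.3% | 6.2% |
| 0% vs 20% | 38.3% | 57.9% |
| 5% vs 20% | 19.8% | 26.8% |
| 5% vs 30% | 54.9% | 62.6% |

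For 80% power with 0% in one arm, the other arm needs a rate of 30% with Fisher and 25.5% with Boschloo.

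**Step 5: other arm sizes, 0% versus 20%.**
- 25/25, 24/25 and 26/26: a gain of about 20 points.
- 24/26 and 23/25: a gain in one direction only. At 24/26 power goes from 42% to 62% when the 20% rate is in the 26-eye arm, and is unchanged the other way.
- 24/24, 23/23 and 23/24: essentially nil. At 24/24 Fisher already calls 5-0 significant: 2 × C(24,5)/C(48,5) = 2 × 42,504/1,712,304 = 0.0496. Power is 54% with either test.

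Boschloo lost no Fisher rejection at any arm-size pair checked.

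**Step 6: fellow eyes.** Boschloo's size guarantee assumes independent eyes. With 6, 12 or 25 bilateral participants whose two eyes always agree, its maximum size was 4.5%, 4.5% and 4.2%.

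**The case against.** Fisher's test is valid, pre-specified and familiar, and it controls type I error. It is also the permutation test for a 2 × 2 table, so it matches the permutation approach of the primary analysis. The SAP claims no power for these outcomes, and Protocol 1.1 places long-term graft rejection and survival beyond the initial phase. All of this stands, and it is why the point is not an error in the plan.

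The size of the gain can also be challenged. The 20-point figure needs a 20% rate in one arm and none in the other, rates the documents do not supply. It disappears if one eye is lost from each arm. Exactly 25/25 is not assured: randomisation uses random block sizes, and SAP section 4 expects that some participants may have no follow-up data. This stands too and limits the claim.

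Finally, Boschloo's guarantee rests on independent binomial sampling, while fellow eyes may both enter. The extreme-concordance check in step 6 is reassuring, but it is a check and not a proof.

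What the objection does not show is any setting in which the change costs power or breaks the 5% limit with independent eyes.

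**Conclusion.** This is a cheap improvement that is worth making. At 25 eyes per arm Fisher's test runs below 1% size for common rates up to 10%. Boschloo's test recovers part of the lost power: roughly 4 to 20 points in the 25/25 scenarios tried, less or none at some other arm sizes, and never a loss.

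A reader might infer three stronger things, none of which is supported.
- That Fisher's test is wrong here. It is valid, and the SAP promises no power for these outcomes.
- That Boschloo recovers all of the lost power. It stays conservative at low rates (0.41% size at a 5% rate), and power for 2% versus 10% is still only 6%. Few events in 25 eyes per arm are the main limit.
- That a 20-point gain can be counted on. It depends on the assumed rates and the final arm sizes.

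The conclusion rests on a two-sided 0.05 level, which the SAP states only for the primary analysis, and on assumed event rates.

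**What to change.** In SAP section 5, name the two-sided Boschloo exact unconditional test at 0.05, in place of Fisher's, for primary graft failure and graft rejection. Add the risk difference with a 95% exact unconditional confidence interval for each; this is useful whichever test is kept.

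Define the test fully: tables ordered by the two-sided Fisher p-value, with the arm sizes as the fixed margin. Unlike Fisher's, this p-value changes if rows and columns are swapped in software. For 4 against 0 at 25/25 it is 0.065 with the arms as the fixed margin, but 0.049 in a routine given the transposed table.

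Do not offer the Fisher mid-p value as an equivalent. Its 5% limit is not guaranteed: the maximum size is 5.01% at 23/24 and 5.05% at 25/26. These excesses are trivial, but the guarantee is gone.

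The cost is a few words in the SAP and a different software call. The downsides are a less familiar test and a size guarantee that assumes independent eyes, which the SAP should acknowledge. The change must be made before outcomes by arm are seen, because switching tests after a 5-0 result would not be credible.

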1.2 Study Outcomes

Primary Outcome:

- BSCVA at 6 months

Secondary Outcomes:

- Endothelial cell counts
- Corneal higher-order aberrations as measured by Pentacam
- Interface haze as measured by Pentacam densitometry
- Change in NEI-VFQ *from baseline to 3 months and 12 months*
- Primary graft failure, defined as a lack of graft clearing or need for re-graft within the first 2 months
- Graft rejection, defined as loss of graft clarity due to edema with evidence of inflammation such as anterior chamber cell or keratic precipitates.

Other Outcomes measured:

- Refraction
- Graft thickness as measured by OCT and pachymetry
- Operative times
- Adverse events/Complication rates

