3.2.2 Eligibility criteria for study participants

Only those who meet all of the inclusion criteria and none of the exclusion criteria will be enrolled in this study.

Inclusion Criteria:

- Damaged or diseased endothelium from Fuchs or Pseudophakic Bullous Keratopathy
- Good candidates for corneal transplantation for either DMEK or DSAEK
- Willingness and ability to undergo a cornea transplantation
- Willingness to participate in follow-up visits

Exclusion Criteria:

- Participants who are decisionally and/or cognitively impaired
- Participants who are not suitable for the DMEK or DSAEK surgeries
- Prior Endothelial Keratoplasty (EK) or any other ophthalmic surgery except uncomplicated cataract surgery

- Indication for surgery that is not suitable for EK (e.g. keratoconus, stromal dystrophies and scars)
- Presence of a condition that increases the probability for failure (e.g., heavily vascularized cornea, uncontrolled uveitis)
- Other primary endothelial dysfunction conditions including posterior polymorphous corneal dystrophy and congenital hereditary corneal dystrophy
- Aphakia, or anterior chamber IOL in study eye prior to or anticipated during EK
- Planned intraocular lens exchange of an anterior chamber IOL with a posterior chamber IOL in study at time of study EK
- Pre-operative central sub-epithelial or stromal scarring that the investigator believes is visually significant and could impact post-operative stromal clarity assessment
- Peripheral anterior synechiae (iris to angle) in the angle greater than a total of three clock hours
- Hypotony (Intraocular pressure <10mmHg)
- Uncontrolled (defined as intraocular pressure >25mmHg) glaucoma
- Visually significant optic nerve or macular pathology

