4.4 Study Schedule

Table 1: Study Schedule

	Visit 1 Pre-op	Visit 2 Surgery	Visit 3 Month 3	Visit 4 Month 6	Visit 5 Month 12	Visit 6 Month 24
Forms						
Consent and Authorization form	X					
Baseline form	X					
NEI-VFQ	X (for 1 st eye)				X	
Follow-up form			X	X	X	X
Final form						X
Procedures						
DMEK or DSAEK surgery		X				
Tests						
IOP	X		X	X	X	X
Pachymetry U/S	X		X	X	X	X
Pentacam (densiometry & topography)	X		X	X	X	X
OCT			X	X	X	X
Endothelial imaging			X	X	X	X
Slit Lamp Photography*	A few patients			X		
BSCVA/ETDRS/MRx	X		X	X	X	X
Total visit time	2 hours	2 hours	1 hour	1 hour	1 hour	1 hour

* Slit lamp photography also taken upon an adverse event

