- We will also look at BSCVA at using a last observation carried forward (LOCF) analysis. For study participants who experience primary graft failure and must undergo re-graft, graft failure will be noted and a BSCVA will be performed prior to performing further surgery. This last observation will be carried forward as the 6 month BSCVA.
- We will conduct the Kolmogorov-Smirnoff test to compare the 6-month (BSCVA) distribution between DMEK and DSAEK arms.
- Interface haze as measured by Pentacam densitometry will be analyzed using a Wilcoxon rank sum test.
- Corneal higher-order aberrations as measured by Pentacam will be analyzed using a Wilcoxon rank sum test.
- We will also perform a cost-effectiveness analysis of the clinical trial data, according to the protocol provided in the Supplementary Cost Effectiveness Analysis Statistical Analysis Plan.

6. Other Data

Other data to be collected include manifest refraction, graft thickness as measured by OCT, pachymetry, operative times, and adverse events or complications.

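### Pentacam higher-order aberrations are compared without baseline adjustment, although a pre-operative scan is scheduled and the SAP already has rank ANCOVA: an optional gain in precision, not an error

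*SAP*

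**What the plan says.** - **Outcome.** Protocol 1.2 lists among the secondary outcomes "Corneal higher-order aberrations as measured by Pentacam". Aim 3 in Protocol 1.1 predicts "no difference in posterior corneal higher-order aberrations of the central 4mm in DSAEK versus DMEK".
- **Planned test.** SAP section 5, under the supplementary secondary outcomes: "Corneal higher-order aberrations as measured by Pentacam will be analyzed using a Wilcoxon rank sum test". No covariate is named. Interface haze, also from the Pentacam, gets the same test.
- **Baseline scan.** Protocol 3.4.1: "Patients will also complete BSCVA, IOP, Pachymetry, and Pentacam tests at baseline". In Table 1 of Protocol 4.4 the row that begins "Pentacam (densiometry & topography" is marked at the pre-operative visit and at months 3, 6, 12 and 24.
- **Rank ANCOVA.** As a sensitivity analysis of the primary outcome, SAP section 4 says "we will conduct ANCOVA with ranks (which becomes the Wilcoxon rank sum test in the post-test only case".
- **Omission rule.** SAP section 4: "If the correlation coefficient between baseline BCVA and 6 month BCVA has magnitude less than 0.1, we will omit the variable entirely".
- **Other outcomes.** The SAP also adjusts three-month acuity, endothelial cell count and NEI-VFQ for a baseline value.

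**The concern.** The trial plans to scan every eye before surgery, but the aberration analysis does not use that scan. The SAP has the method at hand: rank ANCOVA becomes the planned Wilcoxon test when no covariate is used, and a rule for discarding a weak baseline is already written. If pre- and post-operative aberrations are correlated, the unadjusted test gives away precision.

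This matters most for Aim 3. It predicts no difference in posterior aberrations, and what informs such a prediction is how tightly the difference is estimated. With about 25 eyes per arm, that estimate will be loose.

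**Working it through.** **Inputs.** From the documents: 25 eyes per arm (SAP section 2) and a two-sided alpha of 0.05 (stated in SAP section 4 for the primary test and used here). The documents give no SD, effect size, power or pre/post correlation for aberrations, so there is no plan figure to reproduce; the sample-size statement concerns visual acuity only. Assumed: r from 0 to 0.5, a shift of 0.8 SD, bivariate normal data and independent eyes. Rank results do not change if the data are exponentiated, so skewness of that kind does not affect them.

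**Step 1: variance.** Adjustment multiplies the variance of the group difference by (1 - r²). Estimating the slope costs a factor of 1 + 1/46, where 46 = 50 - 4. The net ratio is (1 - r²)(1 + 1/46), and the equivalent number of eyes per arm is 25 divided by that ratio. At r = 0.3, for example: 0.91 × 1.0217 = 0.9298, and 25/0.9298 = 26.9. Break-even is at r = √(1 - 46/47) = 0.146.

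**Step 2: power.** Simulation with 20,000 trials per cell compared the exact Wilcoxon test with rank ANCOVA under the SAP's 0.1 omission rule.

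| r | Net variance ratio | Equivalent eyes per arm | Exact Wilcoxon | Rank ANCOVA with rule | Change (points) |
|---|---|---|---|---|---|
| 0 | 1.0217 | 24.5 | 0.772 | 0.764 | -0.8 |
| 0.15 | 0.9988 | 25.0 | 0.769 | 0.770 | +0.1 |
| 0.3 | 0.9298 | 26.9 | 0.766 | 0.794 | +2.8 |
| 0.5 | 0.7663 | 32.6 | 0.771 | 0.859 | +8.8 |

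Type I error is about 5%. The simulation error of each power is √(0.77 × 0.23/20,000) = 0.003, or 0.3 points. Wilcoxon power does not depend on r, so the spread in that column is simulation noise. A separate simulation without the omission rule gave 0.764 against 0.771 at r = 0, 0.797 against 0.773 at 0.3 and 0.862 against 0.773 at 0.5. These are changes of about -0.6, +2.4 and +8.8 points.

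**Step 3: interval width.** The mean half-width of the 95% interval is 0.588 SD for the Hodges-Lehmann interval that goes with the Wilcoxon test. For rank ANCOVA it is 0.585 SD at r = 0, 0.563 at 0.3 and 0.515 at 0.5. Relative to r = 0, the narrowing is about 4% (0.563/0.585 = 0.962) and 12% (0.515/0.585 = 0.880).

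**Step 4: missing baselines.** Assume two per arm, missing at random. If those eyes stay in with a filled-in covariate value, the ratio is (1 - 0.92r²)(1 + 1/46), where 0.92 = 23/25. This gives 24.5, 25.0, 26.7 and 31.8 equivalent eyes per arm at r = 0, 0.15, 0.3 and 0.5. If they are dropped, 23/[(1 - r²)(1 + 1/42)] gives 22.5, 23.0, 24.7 and 30.0. At r = 0.3, dropping them cancels the gain.

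**Step 5: two eyes per patient.** Protocol 3.4.2 randomizes each eye independently. With an assumed 6, 12 or 20 bilateral patients, inter-eye correlation 0.5 or 0.8 and r = 0.3, type I error was 0.043 to 0.048 for the Wilcoxon test and 0.046 to 0.053 for rank ANCOVA.

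**The case against.** The strongest reply is that nothing here is wrong. The Wilcoxon test is valid in a randomized comparison, the outcome is supplementary, and the SAP confines rank ANCOVA to acuity. Adjusting the key secondary outcomes while giving the Pentacam outcomes simple rank tests is a coherent choice. This stands: a reader might infer a bias or an internal contradiction, and the documents show neither.

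Second, the benefit rests on an unknown r. Surgery alters the posterior surface, the one that Aim 3 names, so r there may be near zero. This also stands. Below about 0.15 there is nothing to gain, and at r = 0 there is a small loss. The omission rule limits the loss only in part: its 0.1 cut-off lies below the break-even of 0.146, and in simulation it removed the covariate in only 50 to 51% of trials at r = 0.

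Third, a reader might take the baseline values as already in hand. The protocol lists a Pentacam examination with densitometry and topography. Whether the same aberration measure is recorded before surgery is a matter for the Pentacam Protocol, a separate document (Protocol 10.2). Feasibility is likely but unconfirmed.

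Fourth, Aim 3 has no margin for aberrations, so a half-width of 0.56 rather than 0.59 SD may change no conclusion. That is fair at r = 0.3 and less so at 0.5.

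None of this removes the point. The loss is under one power point, the possible gain is several, and the method is already in the SAP.

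**Conclusion.** An optional improvement. The unadjusted Wilcoxon test may leave precision unused: no gain below r of about 0.15, about 3 power points at 0.3 and about 9 at 0.5, against a loss of under one point if r is near zero. These figures assume a 0.8 SD shift, 25 eyes per arm, normal data and independent eyes; r itself is not in the documents. The primary result is unaffected.

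A reader might extend the point to interface haze, since it shares the instrument and the test. The documents do not support that. Protocol 3.2.2 excludes "Prior Endothelial Keratoplasty (EK) or any other ophthalmic surgery except uncomplicated cataract surgery", so no graft-host interface exists before surgery, and the unadjusted test is a reasonable choice there.

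**What to change.** Before unmasked aberration data are examined, and once the Pentacam Protocol is confirmed to record the same measure pre-operatively, amend SAP section 5 as follows:

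- Analyse aberrations with the SAP's rank ANCOVA, using the pre-operative value of the same Pentacam measure as covariate.
- Omit that covariate under the SAP's existing 0.1 correlation rule.
- Keep eyes with a missing baseline in the analysis, for example by giving them one covariate value common to both arms.
- Retain the Wilcoxon test as the sensitivity analysis.
- Leave interface haze on the Wilcoxon test.

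The cost is two or three SAP sentences, with no new visit or measurement if the confirmation succeeds. The statistical cost is about 0.8 power points if r is zero. If the same measure is not recorded pre-operatively, the planned Wilcoxon test should stand.
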